### **2.3 Aims and objectives**

The aim of this trial is to assess the safety profile of an ancientbiotic (Bald's salve), when applied to the skin of healthy human volunteers.

#### **2.3.1 Objectives**

The objective is to determine the frequency and character of adverse events associated with a patch test of Bald's salve applied to the skin of 90 to 100 human volunteers.

## **2.4 Outcome measures**

### **2.4.1 Safety profile of ancientbiotic**

#### **Primary Outcome:**

Frequency (prevalence) and character of adverse events at 48 hours after application of 100 µl ancientbiotic on a sticking plaster applied to the upper arm.

**Follow-up:** No further follow-up beyond 48 hours. If there is no skin reaction within 48 hours, we do not anticipate any longer term adverse events. However the study email account will be kept open for up to three months and participants will be advised to contact us if any suspected later reaction occurs.

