## 1.5 Need for a pilot safety trial

A pilot clinical trial will be conducted with approximately 100 healthy adult volunteers, to assess the safety and tolerability of the ancientbiotic product on human skin. We want to find out whether, after completion of laboratory tests to human cells, there is any suspicion that the ancientbiotic causes inflammation to human cells. We consider this highly unlikely given (1) the data from cytotoxicity, irritation and wound healing assays cited above; and (2) that the product consists entirely of edible household ingredients.

**Study Design:** non-randomised, uncontrolled, Phase I pilot trial.

**Participants:** Adults aged 18-79 years, community-dwelling, male or female, without a diagnosis of diabetes, immune-related disease (asthma, eczema, psoriasis), pregnancy, or recent infection will be recruited. People with known dietary allergies will be excluded. People with Covid-19 infection, Covid-19 symptoms, or who are self-isolating due to Covid-19 exposure, will be excluded.

**Intervention:** Sticking plaster infused with one drop of the liquid Bald's salve ancientbiotic compound, applied to the skin of the upper arm, worn for 48 hours.

**Outcomes:** Adverse skin effects over 48 hours e.g. redness, heat, swelling or other. Type, number (%) and spread/distribution will be recorded. Digital photographs will be taken of any suspected skin reaction.

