## 2.8 Consent

**Confirmation of eligibility, and participant approach:**

1. Volunteer contacts the study team expressing interest in the study.
2. Trial team undertake eligibility screening and volunteer provided with Participant Information Sheet (PIS).
3. Allowed 48 hours to consider participation and ask any questions they may have.
4. Potential participant contacted by email, or phone by a member of the research team.
5. Signed consent obtained via post or at clinic.

**Informed consent:** volunteers will be invited to a clinic appointment where consent will be taken in person by an appropriately trained member of the clinical or research team.

**Adults lacking capacity:** will be excluded from the study.

**GP notification:** We do not intend to inform the participant's GP. It will be up to each participant to inform their own GP that they are taking part in the study. We recommend that anyone experiencing signs of persistent skin irritation, lasting after washing/ beyond 48 hours, should contact their GP.

**Timing of consent:** Written informed consent will be obtained by a suitably trained member of the research team (FH/JB) at the Warwick Medical School, after allowing sufficient time for the potential

participant to consider their decision and ask questions about the study. Sufficient time for some potential participants may result in a decision to take part in the trial immediately after receiving all the relevant information. Alternatively, if potential participants would like to leave with the information and decide later, they will be free to do so, and can contact the research team at a later time.

**New information:** We do not anticipate any new information arising that may affect participants' willingness to take part in the study. We will stagger administration initially. If any significant adverse events arise in the first 10 participants, then the study will be halted and the sponsor informed immediately. If minor skin reaction or no reactions occur over 48 hours for the first 10 volunteers, we will continue to roll out administration to the remaining volunteers.

**Decline/withdrawal:** Participants will have the option to withdraw before treatment starts, if for any reason they change their mind. The participant will remain free to withdraw at any time without giving reasons.

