## 3.2 Long term follow-up

Not applicable. We do not anticipate any longer term adverse events beyond 48 hours. However, we will keep the resource email account open for a period of three months beyond the end of recruitment and advise participants they can contact the study team by email if any suspected adverse event occurs in the longer term.

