**Table 2. SAE Causal relationship**

Relationship to trial medication	Description
----------------------------------	-------------

Unrelated	There is no evidence of any causal relationship
Unlikely to be related	There is little evidence to suggest there is a causal relationship (e.g. the event did not occur within a reasonable time after administration of the trial intervention). There is another reasonable explanation for the event (e.g. the patient's clinical condition, other concomitant treatment).
Possible relationship	There is some evidence to suggest a causal relationship (e.g. because the event occurs within a reasonable time after administration of the trial intervention). However, the influence of other factors may have contributed to the event (e.g. the patient's clinical condition, other concomitant treatments).
Probable relationship	There is evidence to suggest a causal relationship and the influence of other factors is unlikely.
Definitely related	There is clear evidence to suggest a causal relationship and other possible contributing factors can be ruled out.

To establish causality, the following information should be collected for each SAE:

- full details in medical terms and case description
- event duration (start and end dates, if applicable)
- action taken
- outcome
- seriousness criteria
- causality (i.e. relatedness to intervention), in the opinion of the CI
- whether the event would be considered expected or unexpected.

SAEs that are deemed to be unexpected and possibly, probably or definitely related to the trial interventions or outcomes assessments, will be notified to the Research Ethics Committee (REC) within 15 days. All such events will be reported to the wider research group. All SAEs that occur between the date the intervention is delivered and 48 hours will be reported. We do not anticipate new adverse events to occur beyond 48 hours if none are apparent within 48 hours. Nevertheless, the resource account email address will remain active for three months beyond the end of the last 48 hour follow-up.

Any change of condition or other follow-up information should be communicated to the Sponsor as soon as it is available or at least within 24 hours of the information becoming available. Events will be followed until resolution or a final outcome has been reached. A member of the study team will be instructed to closely monitor each participant who experiences a SAE, until the outcome of the SAE has been determined.

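### No active contact is planned after the 48-hour reading, so late or persisting reactions are found only if volunteers report them, and the SAE reporting passages disagree about events after 48 hours

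*Protocol*

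**What the plan says.** Section 1.5 describes the plaster as "applied to the skin of the upper arm, worn for 48 hours". Section 2.4.1 defines the primary outcome as "Frequency (prevalence) and character of adverse events at 48 hours after application of 100 µl ancientbiotic", followed by "No further follow-up beyond 48 hours". The reason given there is: "If there is no skin reaction within 48 hours, we do not anticipate any longer term adverse events". Table 1 (section 3.1) ends at Day 2, and section 3.3.1 limits symptom capture to the first 48 hours.

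Two routes are described for anything later. Section 3.2 (Long term follow-up) keeps an email account open for three months and will "advise participants they can contact the study team by email if any suspected adverse event occurs in the longer term". Section 2.8 recommends that "anyone experiencing signs of persistent skin irritation, lasting after washing/ beyond 48 hours, should contact their GP". The same section says the team will not itself notify GPs, and section 1.6 says medical records will not be accessed.

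On serious events, the text after Table 2 in section 3.4 says "All SAEs that occur between the date the intervention is delivered and 48 hours will be reported". The opening of section 3.4, the annual-reporting paragraph and section 3.5 speak of all SAEs, and section 3.6 of any death, none with that limit.

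**The concern.** The objective in section 2.3.1 is how often adverse events follow the patch test and what they are like. It carries no 48-hour limit. The only planned reading falls at the planned end of wear, so what happens to the skin afterwards is left to volunteers to report.

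Two kinds of information are at risk: reactions that first appear after 48 hours, and the course of reactions still present at 48 hours. The protocol treats both as possible, since it gives advice for irritation lasting beyond 48 hours and keeps a mailbox open for late reports. In a study whose sole purpose is safety, a reader could take silence after 48 hours for absence of reaction, which the design cannot support.

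There is also a practical problem. If the mailbox brings news of a serious event after 48 hours, the protocol does not give one consistent account of how it is handled.

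**Working it through.** The plan has no figure to reproduce: section 5.1 states that no sample size was calculated. The check is mainly a comparison of passages.

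**1. Wear and observation**
- Planned wear: 48 hours (section 1.5).
- Outcome reading: 48 hours after application (section 2.4.1).
- The Study Summary lists 48 hours of treatment and 48 hours of follow-up. Section 2.4.1 shows that these are the same 48 hours and not consecutive periods.
- Planned active contacts after the 48-hour one: none (section 2.4.1, Table 1).

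**2. The stated reason against the volunteers it covers**
- Section 2.4.1, and the text after Table 2, expect no later events provided nothing has appeared by 48 hours. That says nothing about a volunteer who does have a reaction at 48 hours.
- Section 3.2 drops the condition and expects no later events at all. Section 2.8 foresees irritation that persists past 48 hours.
- Following events to resolution appears only in the SAE text of section 3.4. Nothing comparable is stated for a non-serious skin reaction, which is the kind of event section 3.3.1 expects.

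**3. How later information reaches the study**
- Late onset: volunteer-initiated contact only.
- Persistence: volunteer-initiated contact, or a GP visit. The GP visit has no return path to the study unless the volunteer creates one.

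**4. SAE wording**

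| Place | Time limit |
|---|---|
| Section 3.4, opening | none; recorded within 24 hours of awareness |
| Text after Table 2, reporting window | delivery to 48 hours |
| Text after Table 2, notification to the REC of unexpected, related SAEs | none on onset; within 15 days |
| Annual reporting | none |
| Section 3.5 | none; within 24 hours of awareness |
| Section 3.6 | any death, though it calls the study period 48 hours |

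**5. Illustration of size**

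The documents give neither the share *p* of volunteers who react only after 48 hours nor the share *c* of those who would report it unprompted. Both are assumed here, with *n* = 90 to 100 from section 2.2.

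Chance that at least one late case occurs: 1 − (1 − *p*)^*n*. Chance that the study hears of at least one: 1 − (1 − *pc*)^*n*.

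| *p* | Occurs, *n* = 100 | Occurs, *n* = 90 | Heard of, *n* = 100, *c* = 0.25 to 0.5 |
|---|---|---|---|
| 1% | 63% | 60% | 22% to 39% |
| 2% | 87% | 84% | 39% to 63% |
| 5% | 99% | 99% | 72% to 92% |

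If no reaction were seen by 48 hours, the one-sided 95% upper bound on the rate would be 1 − 0.05^(1/*n*): 3.0% for *n* = 100 and 3.3% for *n* = 90. That bound applies to reactions up to 48 hours and says nothing about later ones.

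**The case against.** The strongest reply is that this is an openly stated design choice in a small pilot, with some basis. Section 1.3.2 reports corneal irritation that cleared within ten minutes, and no visible irritation in mice treated daily for 15 days. Volunteers receive a study telephone number and email address for prompt advice (section 1.6), so the GP is an additional route and not the only one, and volunteers may tell their GP about the study. Contact can be chased for up to ten days (section 2.10.2), and someone who removes the plaster early because of discomfort (section 1.8) is still contacted after 48 hours. Some observation after removal will therefore occur.

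All of that stands, and it limits the point. It does not remove it: the preclinical results are not human data after patch removal, the ten days are a tolerance for non-responders, and the telephone and mailbox depend on the volunteer acting.

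The reply also defeats several stronger readings that a reader might infer.

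- *That a late SAE known to the team is excluded from reporting.* Other passages run from awareness or carry no time limit. The text conflicts with itself; it does not cleanly exclude such an event.
- *That late reactions have no denominator or no place in the analysis.* Everyone patched is the denominator. The secondary outcome in the Study Summary and the analysis text in section 5.2.3 are not limited to 48 hours. What is incomplete is the late numerator.
- *That the primary result is biased.* That outcome is defined at 48 hours, so later reactions are a different quantity.

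**Conclusion.** The concern holds in a limited form. The plan answers its objective by active enquiry only up to 48 hours; beyond that, ascertainment is passive and incomplete, and the stated reason for stopping does not reach volunteers who have a reaction at 48 hours. This rests on the protocol's own text and not on the illustrative rates. How many reactions would be missed cannot be estimated from the documents. Over the assumed range of 1% to 5% late reactors among 100 volunteers, with a quarter to a half self-reporting, the chance of hearing of any runs from 22% to 92%, so silence after 48 hours would be weak evidence of no reaction.

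The SAE wording is a separate internal conflict that needs reconciling. The 48-hour primary outcome is sound as defined. Both changes are worth making and neither alters the design.

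**What to change.** 1. In section 2.4.1, Table 1 and section 3.2, add one scripted text or email to every volunteer a few days after plaster removal, with the exact day set by the sponsor. Ask about any new or ongoing skin reaction and the date it resolved, with a photograph if the answer is yes. Report late-onset and ongoing reactions as a secondary outcome over all patched volunteers, with the number who did not reply. Leave the 48-hour primary outcome unchanged.

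2. Reconcile the 48-hour SAE sentence after Table 2 with the opening of section 3.4, the annual-reporting paragraph, sections 3.5 and 3.6, and the three-month mailbox, so that it is clear how an SAE the team learns of after 48 hours is handled.

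The cost is about 100 messages over contact routes that already exist (sections 2.2 and 2.9.2), a short amendment, and some non-response at the second contact. No visit is added.

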### **2.4.2 Safety**

The study will be delivered in Warwick Medical School and School of Life Sciences, University of Warwick. See section 4.0 for AE and SAE information.

## **2.5 Eligibility criteria**

Volunteers are eligible to be included in the study if they meet the following criteria:

### **2.5.1 Inclusion criteria**

1. Adults aged 18 years to 79 years.
2. Not known to be pregnant.
3. No history of asthma, eczema, psoriasis, known allergies e.g. to food stuffs, sticking plasters or other allergies, no broken skin on the upper arms.
4. No recent infection in previous 3 months, including Covid-19 infection.
5. Willing to provide signed consent to participate in the study.
6. Fluent in spoken English to allow engagement with study.
7. Willing to be contacted by telephone, email or video-based platform at follow-up.
8. Willing for the research team to hold a photographic image if any skin irritation occurs.

### **2.5.2 Exclusion criteria**

1. Pregnancy.
2. Diabetes.
3. Any known allergies or recent infection (within 3 months).
4. Any skin condition, including eczema or psoriasis or broken skin.
5. Any diagnosis of asthma.
6. Unable to be contacted by email, phone or video platform within 48 hours of intervention delivery.

## 2.6 Participant identification / Screening

**Participant identification:** Volunteers will be identified and screened by the research team:

1. *University of Warwick staff and students:* via advertisement to student groups, before lectures, email circulars to Warwick Medical School and staff from other sections.
2. *Community-based recruitment:* local volunteer groups, Women's Institute (WI), self-referral. The study was advertised during an external event to the WI and people expressed an interest in participating.

A website will be developed, hosted on the University of Warwick server, with information on the study and the participant information sheet (PIS) in downloadable PDF format.

## 2.7 Staff Training

Up to three members of the study team ([name] (CI), [name], + research assistant under appointment) will be responsible for the administration of the ancientbiotic liquid and application of the sticking plaster. Staff have completed relevant continued professional development (CPD) and good clinical practice (GCP) training. The trial team ([name]/[name]) have tested application of the intervention as pre-pilot testing. The clinic will be held over a period of one week initially.

## 2.8 Consent

**Confirmation of eligibility, and participant approach:**

1. Volunteer contacts the study team expressing interest in the study.
2. Trial team undertake eligibility screening and volunteer provided with Participant Information Sheet (PIS).
3. Allowed 48 hours to consider participation and ask any questions they may have.
4. Potential participant contacted by email, or phone by a member of the research team.
5. Signed consent obtained via post or at clinic.

**Informed consent:** volunteers will be invited to a clinic appointment where consent will be taken in person by an appropriately trained member of the clinical or research team.

**Adults lacking capacity:** will be excluded from the study.

**GP notification:** We do not intend to inform the participant's GP. It will be up to each participant to inform their own GP that they are taking part in the study. We recommend that anyone experiencing signs of persistent skin irritation, lasting after washing/ beyond 48 hours, should contact their GP.

**Timing of consent:** Written informed consent will be obtained by a suitably trained member of the research team (FH/JB) at the Warwick Medical School, after allowing sufficient time for the potential

participant to consider their decision and ask questions about the study. Sufficient time for some potential participants may result in a decision to take part in the trial immediately after receiving all the relevant information. Alternatively, if potential participants would like to leave with the information and decide later, they will be free to do so, and can contact the research team at a later time.

**New information:** We do not anticipate any new information arising that may affect participants' willingness to take part in the study. We will stagger administration initially. If any significant adverse events arise in the first 10 participants, then the study will be halted and the sponsor informed immediately. If minor skin reaction or no reactions occur over 48 hours for the first 10 volunteers, we will continue to roll out administration to the remaining volunteers.

**Decline/withdrawal:** Participants will have the option to withdraw before treatment starts, if for any reason they change their mind. The participant will remain free to withdraw at any time without giving reasons.

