### **2.2 Trial summary**

Trial overview: Healthy volunteers will be sought by the research team using multiple strategies, including email circular invitations, social media and advertising the study to University of Warwick staff and students during academic term time. We will also seek a broad range of volunteers and will also recruit from the local community via groups (e.g. Women's Institute, activity groups) who have learned of the study via the media or our outreach activities (e.g. FH invited talks planned for January 2021). We will only recruit volunteers who are based in the surrounding locality (Coventry, Leamington, Warwick and Kenilworth). We aim to recruit between 90 to 100 volunteers in total.

After consent and recruitment, a small drop of the Bald's salve (intervention) will be applied onto a sticking plaster and applied to the participant's upper arm.

A fresh batch of the salve will be prepared using garlic and onions sourced from a commercial greengrocer, Pennard Organic white wine sourced from Avalon Vineyard, Somerset, and bovine bile (Merck Millipore catalogue no. B3883 suspended in sterile water). The salve will be passed through a 0.2µm syringe filter prior to use in this study to ensure sterility.

Outcomes will be captured at 48 hours. Due to Covid-19, face to face assessment of all participants will not be undertaken; this will be replaced with telephone or video contact supplemented with email.

Thus, after 48 hours, the participant will be contacted by the research team and asked to report any sign of skin reaction. We will ask participants to send a photographic image of the affected area. Some participants may be contacted by video (MS Teams, Zoom, Google or other video platform at the participant's discretion) for visual assessment of the affected area. We will collect and store photographs only from those reporting signs of redness or irritation and from a small sample of people with no symptoms (n=5), for comparison purposes.

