## **5 STATISTICAL ANALYSIS**

### **5.1 Power and sample size**

No sample size was calculated for this phase 1 study. The aim is to assess safety of the salve. The primary outcome will be adverse skin effects over 48 hours e.g. redness, heat, swelling or other. Type, number (%) and spread/distribution will be recorded.

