#### **5.2.2 Planned recruitment rate**

We plan to recruit over a period of four weeks. This will be extended if necessary. The first phase will recruit five to ten participants and then, after completion of follow-up, the remainder will be recruited.

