## 6.6 Trial timetable and milestones

**Table 1. Trial timetable and milestones**

Month	Activity	Milestone	Team
-3-0	Ethics submission & approval	Approval	CI/CoCI/RA
1-2	1. Start project 2. Finalise protocol & CRFs 3. Pilot with 5-10 participants	1. Final versions approved	
3	1. Continue recruitment 2. 48 hour follow-up 3. Continue follow-up on all participants	1. Recruit to target Assessment of follow-up rates	CI/CoCI/RA
4-5	End recruitment		
	Statistical analysis		Statistician
	End of study	Final reports	CI/CoCI/RA

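### Section 2.8 holds roll-out until 48 h results are known for the first 10 volunteers, but section 5.2.2 and the timetable allow a first phase as small as five

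*Protocol*

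**What the plan says.** Section 2.8 (Consent, under New information) contains the halt rule: "If any significant adverse events arise in the first 10 participants, then the study will be halted and the sponsor informed immediately". The next sentence gives the condition for continuing. If the reactions are minor, or if "no reactions occur over 48 hours for the first 10 volunteers, we will continue to roll out administration to the remaining volunteers". Both sentences use 10, and both come after a statement that administration will be staggered at first.

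Section 5.2.2 (Planned recruitment rate) says: "The first phase will recruit five to ten participants and then, after completion of follow-up, the remainder will be recruited". The timetable in section 6.6 lists "Pilot with 5-10 participants" in months 1-2 and continued recruitment in month 3. It sets no release condition of its own.

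The total is given in section 2.2: "We aim to recruit between 90 to 100 volunteers in total". Outcomes are taken at 48 hours, and section 2.4.1 states "No further follow-up beyond 48 hours". Section 2.10.2 records a participant as lost to follow-up after at most ten days without contact. No section says which first-phase size prevails.

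**The concern.** One decision, when to move from the first few volunteers to everyone else, has two thresholds in current text. A team that follows 5.2.2 with a first phase of five could open the study to the rest while only half of the group named in 2.8 has been observed. Participants 6 to 10 would still fall under the halt rule, but they would be dosed alongside later volunteers and not ahead of them.

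Section 2.8 is the only prespecified halt-or-continue rule before wider exposure. The protocol has no steering or data monitoring committee (sections 3.5 and 6.9) and no trial management group (section 6.8). The safety results it presents come from cultured cells, bovine eyes, slugs and mice (section 1.3.2). Safety is the trial's sole aim, so its one early gate should have a single size.

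**Working it through.** **1. Comparing the sections.** Minimum number followed for 48 h before release: 10 under 2.8, and 5 under 5.2.2. Section 5.2.2 permits six sizes (5, 6, 7, 8, 9, 10). Only 10 satisfies both sections without interpretation; the other five do not.

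**2. No planned figure to reproduce.** Section 5.1 says "No sample size was calculated for this phase 1 study", and the protocol gives no expected rate of significant events. The rates in step 4 are therefore assumptions, and steps 3 and 4 are illustrations.

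**3. What zero events would show.** The exact one-sided 95% upper bound after 0 events in n people is 1 - 0.05^(1/n).

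| First phase n | 5 | 6 | 7 | 8 | 9 | 10 |
|---|---|---|---|---|---|---|
| Upper bound | 45.1% | 39.3% | 34.8% | 31.2% | 28.3% | 25.9% |

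**4. Chance of seeing at least one event.** This is 1 - (1 - p)^n.

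| Assumed true rate p | n = 5 | n = 10 |
|---|---|---|
| 1% | 4.9% | 9.6% |
| 5% | 22.6% | 40.1% |
| 10% | 41.0% | 65.1% |

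For example, at 10%: 1 - 0.9^5 = 0.410 and 1 - 0.9^10 = 0.651.

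**5. People dosed beyond the tenth before the tenth 48 h result is known.** Under 2.8 this is zero. With release after five, 90 - 5 = 85 to 100 - 5 = 95 volunteers remain. Suppose dosing is evenly paced and 48 h spans two clinic days. The number is then 2 x (remaining volunteers) / (clinic days used).

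- 20 clinic days: 2 x 85/20 = 8.5 to 2 x 95/20 = 9.5
- 15 clinic days: 2 x 85/15 = 11.3 to 2 x 95/15 = 12.7
- 5 clinic days: 2 x 85/5 = 34 to 2 x 95/5 = 38

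This gives about 9 to 13 over 15 to 20 clinic days, and about 34 to 38 over five. The protocol does not give the number of clinic days. Section 5.2.2 plans four weeks of recruitment, while section 2.7 says the clinic runs for one week initially. All three schedules are assumptions, and the answer depends heavily on which is right.

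**The case against.** The best defence is that the sections govern different things: 5.2.2 concerns recruitment and 2.8 concerns administration. Section 2.8 allows signed consent by post, Table 1 in section 3.1 marks written consent before Day 0 as well as on it, and sections 2.2 and 2.10.1 place the salve after consent and recruitment. Volunteers could therefore be signed up after five while dosing beyond the tenth waits. This reading is available, so a reader should not infer that recruiting the remainder must mean dosing them. It is strained, however. Section 5.2.2 makes the remainder wait for follow-up to finish, which makes sense as a gate on exposure and has little purpose for collecting signatures. Section 2.8 also describes consent taken in person at a clinic appointment.

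A second defence is that 5.2.2 is only a planning range, the one clause that says what stops or continues dosing already says 10, and a first phase of 10 satisfies every section. That is true, and it limits the harm. It does not tell staff which number to follow if they choose fewer.

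Third, the probabilities rest on assumed rates, and neither gate was chosen for statistical performance. This stands. At a true rate of 1%, even 10 people show no event about 90% of the time (100% - 9.6% = 90.4%). The figures compare the two gates; they do not validate 10 as a safety threshold.

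**Conclusion.** The point holds as an inconsistency in a decision threshold and should be fixed. Following 5.2.2 with a first phase of 5 to 9 can release the remainder before the condition in 2.8 is met. At the extreme, the group observed before release is halved from 10 to five. The zero-event upper bound then rises from 25.9% to 45.1%, and the chance of detecting a 10% event rate (assumed) falls from 65.1% to 41.0%. How many extra people would be exposed cannot be fixed from the protocol, because it gives no clinic schedule.

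A reader might infer that 5.2.2 removes the halt rule or leaves volunteers without safety oversight. The protocol does not support that. The halt rule still names the first 10, and serious adverse event reporting, chief investigator review and urgent safety measures (sections 3.4, 3.5 and 3.7) apply throughout. Nor is it established that a gate below 10 will be used. The descriptive primary analysis is unaffected.

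**What to change.** In section 5.2.2, set the first phase at 10 participants. In section 6.6, change 5-10 to 10. In section 2.8, add that no further participant is dosed until 48 h outcomes are in hand for 10 participants, and that anyone among the first 10 who withdraws or is lost to follow-up is replaced. Without the replacement clause, one unreachable participant would block release for good. Replacement should cover a missing outcome only: a significant event reported before withdrawal still triggers the halt.

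The cost is one number in each of two sections and a sentence or two in 2.8. Release is delayed by the time needed to dose up to five more people, usually days, though the exact time depends on the clinic pace. It takes longer if one of the first 10 is hard to reach, because contact attempts may run to ten days under section 2.10.2 and a replacement then needs a further 48 h. Section 5.2.2 already allows for a longer recruitment period: "We plan to recruit over a period of four weeks. This will be extended if necessary". Sample size and analysis stay as they are.
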